6.2 Efficacy Endpoints

Response rate will be based on the central review of radiographic assessment of PET-CT scans using the Lugano Classification. DOR, DOCR, PFS and HSCT related endpoints will be based on investigator's review of radiographic assessment of PET-CT scans using the Lugano Classification and clinical assessment.

100 Day non-relapse mortality (NRM) Rate after HSCT

Non-relapse mortality rate at 100 days after HSCT will be estimated using the cumulative incidence function with relapse or deaths due to relapse treated as competing risks. Only subjects who achieve a response **per investigator's review** and undergo autoHSCT are included. Only deaths without relapse are considered as events.

Allogeneic HSCT (alloHSCT) Rate

Allogeneic HSCT rate is the proportion of responder **per investigator's review** (subjects who achieved either CMR or PMR during the treatment) who have undergone alloHSCT **while in remission and without any other anti-cancer treatment**.

Autologous HSCT (autoHSCT) Rate

Autologous HSCT rate is the proportion of responder **per investigator's review** (subjects who achieved either CMR or PMR during the treatment) who have undergone autoHSCT **while in remission and without any other anti-cancer treatment**

Complete Metabolic Response (CMR)

CMR is determined by the central review of radiographic assessment of PET-CT scans using the Lugano Classification. Subject's CMR status is determined by whether the subject achieves CMR during the first 12 weeks of treatment since starting blinatumomab.

Complete Metabolic Response Rate (CMR Rate)

Complete metabolic response rate (CRR) is the proportion of subjects who have achieved CMR by the central review of radiographic assessment of PET-CT using Lugano Classification among all subjects in the respective analysis set.

Duration of Response (DOR)

Duration of Response is calculated only for subjects who achieve a response (CMR or PMR) per **investigator's** review during the first **12 weeks** starting blinatumomab. The duration will be calculated from the date a response, CMR or PMR, is first achieved until the earliest date of a disease assessment indicating disease progression or death, whichever occurs first. **For diagnosis of progression of lymphoma, the progression per investigator's review of radiographic assessment of PET-CT using Lugano Classification will be used. In the absence of radiographic assessment during the long term follow up period, the clinical progression on the CRF page will be used.** Subjects who do not have a relapse event will be censored on their last **radiological non-missing evaluable tumor assessment date or last non-missing clinical assessment**. If the last disease assessment date is after the date that triggers the analysis, the subject will be censored **at the last radiological non-missing evaluable tumor assessment date or last non-missing clinical assessment** prior to the analysis trigger date. A sensitivity analysis will censor subjects who receive a HSCT at the time of HSCT unless there is no assessment after the HSCT, in which case the last **clinical or radiological non-missing evaluable tumor assessment** prior to the HSCT will be used as the censoring time.

HSCT Rate

HSCT rate is the proportion of responder per investigator's review (subjects who achieved either CMR or PMR during the treatment) who have undergone alloHSCT or autoHSCT while in remission and without any other anti-cancer treatment.

Objective Response (OR)

OR is determined **by the central review of radiographic assessment of PET-CT using Lugano Classification**. Subject's ORR status is determined by whether the subject achieves OR (CMR or PMR) during the first 12 weeks of treatment since starting blinatumomab.

Objective Response Rate (ORR)

Objective response rate (ORR) is the proportion of subjects who have achieved an OR (CMR or a PMR) **by the central review of radiographic assessment of PET-CT using Lugano Classification** among all subjects in the respective analysis set.

Overall Survival (OS)

It is calculated as the time from the first dose of blinatumomab until death due to any cause. Subjects who are alive at the date that triggers the analysis will be censored at the date last known to be alive.

Progression Free Survival (PFS)

PFS will be calculated as the time from the date of first dose **of blinatumomab** until the date of diagnosis of progression of lymphoma, or date of death, whichever is earliest.

For diagnosis of progression of lymphoma, the progression per investigator's review of radiographic assessment of PET-CT using Lugano Classification will be used. In the absence of radiographic assessment during the long term follow up period, the clinical progression on the CRF page will be used. Subjects who are alive and did not have progression will be censored at the last clinical or radiological **non-missing evaluable** tumor assessment date.

Successful Mobilization Rate

Successful mobilization rate is **the** proportion of subjects, **among those who initiate mobilization while in remission and without any other anti-tumor therapy**, for whom the mobilization procedure has **an** outcome as 'Successful' as recorded on the mobilization CRF page.

7. Analysis Subsets

The primary analysis of safety will be performed on the Safety Analysis Set.

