- ^h Tumor lysis prophylaxis may be warranted based on results of uric acid testing
- ⁱ In the event of temporary interruption that requires initiation of a new cycle, these tests are not required
- ^j Collect as close as possible to time of event without endangering subject safety
- ^k Bone marrow biopsy is not required if PET scan is negative and if not otherwise clinically necessary by investigator discretion
- ^l Plasma must be collected, processed, and frozen within 4 hours of phlebotomy.
- ^m Blood samples for blinatumomab PK measurement will be taken on day 1 (pre-dose), day 2, day 9, and day 16
- ⁿ Blood samples for cytokine measurement will be taken in subjects receiving blinatumomab on day 1 (predose), day 2 (ie, 24 hours postdose/postdose step), day 8 (pre-dose step), day 9 (ie, 24 hours postdose/postdose step), day 15 (pre-dose and 6 hours post dose step), day 16, and day 57
- ^o Blood samples for lymphocytes will be taken in subjects receiving blinatumomab on day 1 (predose and 6 h), day 2 (ie, 24 hours postdose/postdose step) day 3 (ie, 48 hours postdose/postdose step), day 8 (pre-dose step and 6 hours post dose step), day 9 (ie, 24 hours postdose/postdose step), day 10 (ie, 48 hours postdose/postdose step), day 15 (pre-dose and 6 hours post dose step, and day 16 (ie, 48 hours postdose/postdose step), day 57
- ^p Every attempt should be made to complete PET and CT within 3 days of each other, particularly during treatment
- ^q The Day 70 visit does not necessarily have to happen on the same day as the PET/CT scan. Key endpoint; if subject discontinues study treatment for any reason, including toxicity or clinical evidence of disease progression, PET/CT should be conducted 14 (+ 3) days following the last dose of blinatumomab. Chemotherapy should not be administered within the 14-day treatment-free interval unless clinical evidence of disease progression has occurred and therapy is indicated. Restaging and initiation of cytotoxic chemotherapy should be performed no later than day 70 or 71 of the blinatumomab cycle, ie within 7 days of the end of the treatment-free interval
- ^r Additional lipase and amylase samples should be collected at Investigator discretion if there is suspicion of pancreatitis
- ^s Monitored every 4 to 8 hours dependent upon institution standard of practice and clinical scenario

Approved

Table 7. Schedule of Assessments for Blinatumomab Optional Cycle 2 (Phase 2 and Phase 3)

Day	1	2	3	8	9	10	15	22	29	42

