10.1.1.2 Secondary Endpoint(s)

Key Secondary Endpoints (phase 3 only):

- Overall Survival (OS): calculated as the time from the date of randomization until death due to any cause. Subjects who are alive at the date that triggers the analysis will be censored at the date last known to be alive. If the date last known to be alive is after the date that triggers the analysis, the subject will be censored at the analysis trigger date.

Other Secondary Endpoints:

Phase 2:

- Objective response rates (ORR **including** CMR and PMR)
- PFS: calculated as the time from start of blinatumomab until the date of diagnosis of progression of lymphoma, or date of death, whichever is earliest. Subjects who are alive and did not have progression will be censored at the last date of tumor assessment.
- DOR: calculated only for subjects who achieve an OR. The duration will be calculated from the date a response, CMR or PMR, is first achieved **per central review during the first 12 weeks after starting blinatumomab** until the earliest date of a disease assessment indicating a relapse event or death, whichever occurs first. Subjects who do not have a relapse event will be censored on their last disease assessment date. If the last disease assessment date is after the date that triggers the analysis, the subject will be censored at the analysis trigger date. A sensitivity analysis will censor subjects who receive a HSCT at the time of HSCT unless there is no assessment after the HSCT, in which case the last assessment prior to the HSCT will be used as the censoring time. **Disease assessment during LTFU will be reviewed by investigators only per central review agreement.**
- Successful mobilization rate (defined as CD34+ cell $2 \times 10^6/\text{kg}$)
- HSCT (both autologous and allogeneic) rates among subjects with post-blinatumomab CMR+PMR
- 100-day non-relapse mortality (NRM) after HSCT
- Blinatumomab steady state concentration and clearance
- Incidence and severity of treatment-emergent adverse events

Phase 3:

- OR (**including** CMR and PMR)
- PFS: calculated as the time from the date of randomization until the date of diagnosis of progression of lymphoma, or date of death, whichever is earliest. Subjects who are alive and did not have progression will be censored at the last date of tumor assessment.
- DOR
- Successful mobilization rate (defined as CD34+ cell $2 \times 10^6/\text{kg}$) following protocol assigned therapy

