7.4 Target Dose Analysis Set (TDAS)

All subjects of the FAS who completed at least seven days of infusion on the highest intended dose level will constitute Target Dose Analysis Set (TDAS). In addition, all subjects who discontinue the treatment during the first cycle of treatment due to

progression of disease **per end of treatment reason on CRF** will be included. Primary efficacy endpoint will be analyzed using TDAS.

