10.7.3 Exposure-Response Analysis

PK data of blinatumomab may be subjected to exploratory population PK analysis with data from multiple studies. Nonlinear mixed effects modeling will be used for the analysis. Effect of covariates on exposure will be determined. These may include, age, body weight, body surface area, renal function, liver function, and sex. Other covariates may be analyzed if necessary. Individual blinatumomab exposure at time of interest will be estimated with the population PK model and will be used for the exposure-response (E-R) analysis.

Exposure-response relationships for selected efficacy and safety endpoints may be assessed as appropriate. The objectives and methodology of the exposure-response analysis will be provided in an E-R SSAP.

11. Changes From Protocol-specified Analyses

Per Protocol: Response rates were defined based on radiographic assessment of PET-CT scans using the Lugano Classification. DOR, DOCR, PFS and HSCT related endpoints were based on radiographic assessment of PET-CT scans using the Lugano Classification.

Per SAP: Response rates will be based on **the central review of** radiographic assessment of PET-CT scans using the Lugano Classification. HSCT related endpoints will be based on **investigator's review of** radiographic assessment of PET-CT scans using the Lugano Classification. DOR, DOCR, and PFS related endpoints will be based on **investigator's review of** radiographic assessment of PET-CT scans using the **Lugano Classification and clinical assessment.**

12. Literature Citations / References

Brookmeyer R and Crowley J. A Confidence Interval for the Median Survival Time. *Biometrics*. 1982; 38: 29-41.

Clopper CJ and Pearson ES. The Use of Confidence or Fiducial Limits Illustrated in the Case of the Binomial. *Biometrika*. 1934; 26(4):404-413.

Gao, P, Ware, JH and Mehta, C Sample Size Re-estimation for Adaptive Sequential Design in Clinical Trials, *Journal of Biopharmaceutical Statistics*, 2008; 1184-1196.

Kalbfleisch JD and Prentice R L. *The Statistical Analysis of Failure Time Data*. New York: John Wiley & Sons; 1980.

13. Prioritization of Analyses

Not Applicable

14. Data Not Covered by This Plan

Not Applicable

15. Appendices

Appendix A. Technical Detail and Supplemental Information Regarding Statistical Procedures and Programs

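### SAP 6.2 is inconsistent on clinical progression: its specific PFS and DOR rules admit it only in long-term follow-up, so on-treatment progression without a confirming scan can be missed and PFS can be overstated

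*SAP*

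**What the plan says.** **General statements.** The lead paragraph of SAP 6.2 covers DOR, DOCR, PFS and the transplant endpoints. It says "PFS and HSCT related endpoints will be based on investigator's review of radiographic assessment of PET-CT scans using the Lugano Classification and clinical assessment". SAP Section 11, which lists changes from the protocol, repeats this: "DOR, DOCR, and PFS related endpoints will be based on" the investigator's PET-CT review and clinical assessment. Neither statement is limited to a study period.

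**Specific rule.** The PFS definition in SAP 6.2 says that "the progression per investigator's review of radiographic assessment of PET-CT using Lugano Classification will be used", and then: "In the absence of radiographic assessment during the long term follow up period, the clinical progression on the CRF page will be used". The DOR definition contains the same sentence.

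**Censoring.** For PFS, "Subjects who are alive and did not have progression will be censored at the last clinical or radiological" evaluable tumor assessment. No period limit applies here.

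**Protocol.** Section 10.1.1.2 runs phase 2 PFS from the start of blinatumomab "until the date of diagnosis of progression of lymphoma, or date of death, whichever is earliest", without naming a mode of diagnosis or a period. Table 6 footnote q in Section 7.1 asks for a PET/CT 14 (+3) days after the last dose when treatment stops for any reason, clinical progression included. It also says: "Chemotherapy should not be administered within the 14-day treatment-free interval unless clinical evidence of disease progression has occurred and therapy is indicated".

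**The concern.** The sentence a programmer will code is narrower than the two general statements around it. No rule covers a subject who progresses clinically before long-term follow-up and has no scan showing progressive metabolic disease (PMD).

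The text is also lopsided. A clinical assessment during treatment can set the censoring date, but on the literal rule it cannot be the event. A subject could be censored at the visit that showed the progression. That censoring is informative, because it removes subjects who have just failed.

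PFS is a named secondary objective (SAP 2.2). The trial has a single treated arm, so there is no control group in which a bias of this kind could offset.

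**Working it through.** **Plan's own figure.** The documents give no figure for PFS. The one powered figure is for CMR: 36 subjects, 15% against 40%, one-sided 0.025, 90% power (SAP 3.2). It reproduces with the exact binomial test. Rejecting at 11 or more CMRs gives a type I error of 0.0137 and power of 0.910. Nothing below depends on it.

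**Following one subject.** Take a subject who stops in Cycle 1 with clinical progression and apply the literal PFS rule.

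- Scanned promptly and the scan reads PMD: an event at the scan. Nothing is lost.
- Alive with no scan: not an event at that time. The subject is censored at the last clinical or radiological assessment.
- Scanned after new chemotherapy, and the scan does not read PMD: not an event at that time. The SAP's PFS rule has no provision for new anti-lymphoma therapy, so the subject stays progression-free until something later counts. For response the protocol does have such a provision: Section 6.2.1 scores subjects given chemotherapy before the assessment as nonresponders.
- Dies later, or has clinical progression recorded in long-term follow-up without a scan: an event, but a delayed one.

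Relative to counting the clinical progression when it is recorded, every branch leaves the PFS curve unchanged or raises it.

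**Exposed window.** Treatment lasts about 70 to 112 days (Protocol 3.5.1). The safety follow-up visit comes about 30 days after the last dose, before long-term follow-up.

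**Size at day 70, illustration only.** Assumptions: 36 subjects, k progressors by day 70, no other events or censoring before then, and the affected subjects spread evenly among the progressors.

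Kaplan-Meier: S(70) is the product of (1 − 1/n) over counted events, where n is the number at risk. If all k count, S(70) = (36 − k)/36. Censoring a progressor when n are at risk removes the factor (n − 1)/n, which multiplies S(70) by n/(n − 1).

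| Progressors | Affected | At risk when censored | Day-70 PFS |
|---|---|---|---|
| 12 | 0 | none | 24/36 = 66.7% |
| 12 | 1 | 30 | 66.7% × 30/29 = 69.0% |
| 12 | 3 | 34, 30, 26 | 73.9% |
| 12 | 6 | 35, 33, 31, 29, 27, 25 | 81.9% |
| 18 | 0 | none | 18/36 = 50.0% |
| 18 | 1 | 27 | 50.0% × 27/26 = 51.9% |
| 18 | 3 | 33, 27, 21 | 56.2% |
| 18 | 6 | 35, 32, 29, 26, 23, 20 | 63.0% |

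If an affected subject is instead carried event-free past day 70, each adds 1/36 = 2.8 points.

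**Size on the median, illustration only.** Assume a constant hazard, with a share q of events before day 70 (d = 70/30.4375 = 2.30 months) censored. Then the Kaplan-Meier value at day 70 is the true value raised to the power (1 − q). When the median falls after day 70, it moves by q × d. For q = 10%, 25% and 50%, a true median of 2.5 months reads 2.73, 3.07 and 3.65 months. A true median of 4.0 months reads 4.23, 4.57 and 5.15 months. At q = 0 there is no shift.

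**The case against.** The strongest reply is that the SAP already accepts clinical assessment, in the lead paragraph of 6.2 and in Section 11. The disputed sentence can be read as describing where scans will be absent, and the censoring rule applies only to subjects without progression. This stands in part. It is why the defect is an internal inconsistency with an undefined case, and not a settled decision to exclude on-treatment clinical progression. It does not remove the problem, because the general statements give neither an event rule nor a date.

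Second, a fallback is most needed in long-term follow-up, where PET/CT follows institutional standard (Table 9). In Cycle 1 the scan is marked as a key endpoint and is asked for after any discontinuation. This limits how many subjects can be affected. It does not cover a missed scan, or one taken after the chemotherapy that footnote q permits.

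Third, the protocol names no mode of diagnosis, and Section 7.3.11 assigns response to the Lugano criteria. SAP Section 11 describes the protocol's PFS as PET-CT based, so on its own account the SAP broadened the definition. That is fair, and this point therefore rests on the SAP's own conflict.

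Fourth, SAP 7.4 adds to the target dose set "all subjects who discontinue the treatment during the first cycle of treatment due to" progression, taken from the end-of-treatment reason. A reader might call this a contradiction. It decides membership of an analysis set and neither defines nor dates an efficacy event. It shows only that the CRF records progression in Cycle 1.

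**Conclusion.** The point holds as an inconsistency that can overstate PFS. The bias is upward or zero. It is zero if every clinical progressor is scanned promptly and reads PMD. The DOR rule has the same gap, for example for clinical progression during optional Cycle 2. PFS is summarized descriptively (SAP 10.5.2), so no test, sample size or CMR result is touched.

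A reader might infer more than the documents support:

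- *That PFS is overstated.* This needs subjects whose scan is missed, or follows new therapy and does not read PMD. Their number is not given, and some of their events are delayed rather than lost.
- *That early clinical progression can be estimated at 52%.* In the historical cohort in Protocol 2.1.4, 87 of 55 + 24 + 87 = 166 subjects (52%) had stable or progressive disease. That figure pools two response categories. It carries no progression date and says nothing about missing scans.
- *That each affected subject costs 2.8 points.* This is true only if the subject is carried event-free through day 70. Under censoring, one subject moves the estimate by 2.3 points (12 progressors) or 1.9 points (18).
- *That the gap is a 10-week period with a single scan.* Optional Cycle 2 extends treatment to about 112 days and has its own radiographic assessment at day 42, with PET optional (Table 7).

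**What to change.** In the PFS and DOR definitions of SAP 6.2, remove the words that confine the clinical fallback to long-term follow-up. State that investigator-recorded clinical progression on the CRF, in any period, is the event on its recorded date when no evaluable scan documents progression. This matches the lead paragraph of 6.2 and Section 11.

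Removing the words alone would cover the missing scan. It would not cover the later scan that does not read PMD, because a radiographic assessment then exists. The condition should therefore be worded as no evaluable scan documenting progression.

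Report how many subjects are affected, and give a sensitivity analysis of PFS and DOR under the present wording.

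The cost is a short SAP edit and slightly more programming. Clinical tumor assessments (Protocol 7.3.12) and the end-of-treatment reason are already on the CRF. The reported PFS may be less favourable.

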CMR = complete metabolic response; HSCT = hematopoietic stem cell transplantation; PET-CT = positron emission tomography-computed tomography; PMR = partial metabolic response

a. Subjects with progressive metabolic disease may be eligible after 1 cycle of S1 chemotherapy

Figure 2. Phase 3 Schema

Approved

CMR = complete metabolic response; PMR = partial metabolic response; HSCT = hematopoietic stem cell transplantation; IC = investigator's choice; PET-CT = positron emission tomography-computed tomography; R = randomization; S2 = second salvage

a. Subjects with progressive metabolic disease may be eligible after 1 cycle of S1 chemotherapy

Study Glossary

Abbreviation or Term	Definition/Explanation
¹⁸ FDG-PET	18-fluorodeoxyglucose-positron emission tomography
ABC	activated B-cell
AE	adverse event
ALL	acute lymphocytic leukemia
ALP	alkaline phosphatase
ALT	alanine aminotransferase
ANC	absolute neutrophil count
AST	aspartate aminotransferase
B-NHL	B-cell Non-Hodgkin Lymphoma
CBA	cytometric bead array
CF	cell-free
CT-DNA	circulating tumor DNA
CMR	complete metabolic response
CNS	central nervous system
COO	cell-of-origin
CR	complete response
CRF	case report form
CRS	cytokine release syndrome
CRu	unconfirmed complete response
CSF	cerebro spinal fluid
CT	computed tomography
CTCAE	Common Terminology Criteria for Adverse Events
DILI	drug induced liver injury
DLBCL	diffuse large B-cell lymphoma
DMC	data monitoring committee
DOR	duration of response
EDC	electronic data capture
ECG	electrocardiogram
ECOG	Eastern Cooperative Oncology Group
eCRF	electronic case report form
EFS	event-free survival

Approved

Abbreviation or Term	Definition/Explanation
End of Follow-up	defined as concluding with FA of phase 3 component, which will be triggered by the date when the 236th death of a phase 3 subject is reported in the clinical trial database, or when the study duration reaches 12 months from the last subject randomized, or in the event that the trial does not proceed to phase 3, defined as the date when the last phase 2 subject has had the opportunity to complete their 2 year follow-up after treatment.
End of Study for Individual Subject	defined as the last day that protocol-specified procedures are conducted for an individual subject (ie, the date the subject withdraws full consent from the study, completes the safety follow-up visit or long-term follow up [whichever is later] or death).

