
	Safety follow-up	HSCT	Long-term follow-up	
	Approximately 30 days after last dose of blinatumomab or the last day of the last cycle of IC chemotherapy	Within 14 days prior to conditioning regimen	≤ 2 years after EOT: Every 3 months (± 14 days) ^a	> 2 years after EOT: Every 6 months (± 28 days) ^b
General Assessments				
ECOG Performance Status	X			
Medical history and prior therapies	← Continuous from start of treatment →			
Vital signs	X			
Weight	X			
Physical examination	X			
Neurological exam	X			
Clinical tumor assessment	X	X	X	
Serious adverse events	X		X ^c	
Disease related events	X			
Concomitant medications	X		Lymphoma treatment only	
Subject-reported clinical outcome assessment ^d	X			
HSCT Summary ^e			X ^f	
Local Laboratory Assessments				
Hematology	X			
Chemistry	X			
Coagulation	X			
Immunoglobulins	X			
LDH	X	X	X	
Central Laboratory Assessments				
Bone Marrow ^g		per institutional standard		
Pathology tumor block or slides ^h		Collect if lymphoma relapse		
Plasma sample ⁱ		X	X	
Anti-blinatumomab antibodies	X ^j			
Radiographic Assessments				
PET/CT ^k		per institutional standard		

Footnotes defined on the next page.

Approved

CT=computed tomography; CT-DNA=circulating tumor DNA; ECOG=Eastern Cooperative Oncology Group; EOT=end of treatment; IC=investigator's choice; LDH=; PET=positron emission tomography;

^a To occur in person every 3 months (calculated from safety follow up) until completion of a 2-year period after treatment

^b To occur in person or by telephone call every 6 months (\pm 28 days) until study completion

^c Only adverse events possibly related to blinatumomab will be collected

^d Phase 3 only

^e HSCT summary will include completion of details about mobilization, engraftment, specific toxicities, infectious complications

^f HSCT summary is at first post HSCT visit

^g Bone marrow biopsy is not required if PET scan is negative and if not otherwise clinically necessary by investigator discretion

ⁱ At the time of relapse

^j Plasma must be collected, processed, and frozen within 4 hours of phlebotomy

^k For subjects previously randomized to blinatumomab only

^l Based on any scans performed, response is to be assessed locally according to institutional standard and according to the Lugano classification. Any radiographic indication of progression should be followed-up by biopsy.

Approved

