7.2.7 Long-term Follow-up

For both phase 2 and phase 3, follow-up visits for assessment of relapse, **transplant status**, and survival will take place every 3 months (calculated from the safety follow up visit) until completion of a 2-year period after treatment, **thereafter follow-up for survival and transplant status will** be completed in person or by telephone call every 6 months (\pm 28 days) until study completion. **Study completion will occur** once 236 death events for phase 3 subjects have occurred or 12 months since last subject in phase 3 is randomized if 236th death in phase 3 subjects is not observed. **If the study will not continue for the phase 3 portion, study completion will occur when the last phase 2 subject has had the opportunity to complete their 2 year follow-up visit after treatment.**

Should a subject fail to return to the clinic for a scheduled protocol visit or neglect to participate in a scheduled follow up telephone call, sites will need to make 3 attempts to contact subjects by a combination of telephone and mail. Sites must document all 3 attempts to contact the subject. If a subject does not respond within 1 month after the third contact, the subject will be considered lost to follow-up. The procedures and tests listed in [Table 9](#) will be performed during the long-term follow up. Subjects will allow Amgen continued access to medical records so that information related to subjects' health condition, including disease status and overall survival, may be obtained.

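### One late death can pull the PFS and DOR curves to zero after the 2-year visit, because SAP 6.2 counts late deaths as events but censors living subjects at their last tumor assessment

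*SAP*

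**What the plan says.** **Assessment schedule.** Protocol 7.2.7 schedules relapse, transplant and survival visits every 3 months "until completion of a 2-year period after treatment"; "thereafter follow-up for survival and transplant status will" continue at 6-month intervals. A Table 9 footnote describes these later contacts: "To occur in person or by telephone call every 6 months". No tumor assessment is scheduled in this later period.

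**How long it lasts.** If phase 3 does not go ahead, 7.2.7 says "study completion will occur when the last phase 2 subject has had the opportunity to complete their 2 year follow-up visit after treatment". The Study Glossary entry for End of Follow-up agrees: "defined as the date when the last phase 2 subject has had the opportunity to complete their 2 year follow-up after treatment". Protocol 3.5.2 expects about 12 months of phase 2 enrollment. Protocol 3.5.1, by contrast, gives a phase 2 subject about 30 months in total, with about 2 years of long-term follow-up after the safety visit.

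**Events and censoring.** SAP 6.2 makes death a PFS and DOR event with no limit on the time since the last tumor assessment. SAP 6.1 also provides for deaths found after a subject has left the study, and Protocol 7.3.17 seeks vital status for everyone. For living subjects, the PFS rule is "Subjects who are alive and did not have progression will be censored at the last clinical or radiological" evaluable assessment date, and the DOR rule is similar: "Subjects who do not have a relapse event will be censored on their last" radiological or clinical assessment. The only sensitivity analysis for DOR concerns censoring at HSCT. No rule aligns late deaths with late censoring.

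**The concern.** Kaplan-Meier estimation requires that whether a subject is still at risk at a given time does not depend on what happens to that subject later. After the 2-year visit these rules break that requirement. A living progression-free subject leaves the risk set at about that visit. A comparable subject who dies 5 months later stays in until death. The denominator shrinks to those who will die, so a single death removes most or all of the remaining curve.

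At stake are the late part of the PFS, DOR and duration-of-CMR curves and any quartile read from it. SAP 10.1 reports KM quartiles when estimable. If the curve levels off above 25%, a late death produces an upper-quartile time that would otherwise be reported as not reached. If a small responder subset levels off above 50%, it can produce a median in the same way. In a single-arm study these curves are the evidence on durability.

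**Working it through.** **1. The plan's own duration figure.** Protocol 3.5.1: 28 days of screening + 112 days of treatment + 30 days to the safety visit = 170 days = 5.6 months. Adding 24 months gives 29.6, which reproduces the stated 30-month maximum. On that text follow-up ends about 30 days after the 2-years-after-treatment mark, so there is almost no survival-only period. On 7.2.7 and the Glossary, a subject enrolled at the start of a 12-month accrual waits up to about 12 months more for the last subject. If enrollment is uniform, the mean wait is about 6 months.

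**2. Where the tail begins.** From first dose, the last scheduled tumor visit falls at 70/30.44 + 24 = 26.3 months (70-day treatment) to (112 + 30)/30.44 + 24 = 28.7 months (112 days, counted from the safety visit). This is about 26–29 months.

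**3. Worked example (assumed data).** 36 subjects: 26 early events, 10 event-free at the last tumor visit at 27.6 months, and one of these 10 dies at 32 months without recorded progression.

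- KM at 24 and 28 months under every rule: 10/36 = 27.8%.
- SAP rule: nine are censored at 27.6 months and one is at risk at 32. KM = 27.8% × (1 − 1/1) = 0%, and the upper quartile is reported as 32 months.
- Late death not counted, subject censored at the last tumor assessment: KM stays at 27.8% and the upper quartile is not reached.
- Living subjects kept at risk through survival follow-up: 27.8% × (1 − 1/10) = 25.0%.

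The same mechanism affects a median. With 6 of 10 responders event-free (60%) and one late death, 60% × (1 − 1/1) = 0%, and the date of that death becomes the median.

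**4. How often.** The documents give neither the progression-free share p at the 2-year visit nor the yearly rate h of death without recorded progression, so both are assumed. With the survival-only window uniform on 0 to 1 year, a progression-free subject dies in it with probability q = 1 − (1 − e^−h)/h. This gives q = 0.0099, 0.0246 and 0.0484 for h = 2%, 5% and 10%. The chance of at least one late death among 36 is 1 − (1 − pq)^36:

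| p | h = 2% | h = 5% | h = 10% | simulated: curve ends at exactly 0, h = 5–10% |
|---|---|---|---|---|
| 15% | 5% | 12% | 23% | 12–21% |
| 25% | 9% | 20% | 35% | 19–33% |
| 40% | 13% | 30% | 51% | 28–47% |

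The simulation used n = 36, uniform 12-month accrual and the 2-year visit at about 27 months. A separate run on the same main assumptions, with ±14-day visits, gave ranges reaching 24%, 34% and 48%; hence roughly 12–48% overall. At h = 2% the curve ends at 0 in about 5–12% of trials.

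In a variant where the death hazard runs from first dose, so that fewer subjects reach the 2-year visit, a late death occurred in 5–45% of runs for h = 2–10%. Given one, the curve ended at exactly 0 in 86–89%. For h = 5–10% the product is 0.117 × 0.870 = 10% to 0.446 × 0.886 = 40%. When a late death occurred, the mean final KM was 1–5% under the SAP rule. It was 10–34% with living subjects kept at risk and 14–40% with the late death censored.

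**The case against.** **Later information may exist.** Table 9 allows PET/CT per institutional standard and asks for local Lugano assessment of any scan done. Protocol 7.2.7 gives the sponsor access to records on disease status, and SAP 6.2 accepts clinical progression from the CRF with no 2-year limit. A reader might infer that relapses after 2 years cannot be seen at all. The documents do not support that: such relapses are unscheduled, not invisible, and an unscheduled assessment moves a survivor's censoring date later. This softens the effect, to an extent that cannot be planned, and does not align the two rules.

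**The true tail may be near zero.** Protocol 10.2.2 assumes a median OS of 6.7 months on blinatumomab for phase 3. If survival were exponential, it would be 2^(−27/6.7) = 6% at 27 months, about 2 of 36 subjects. With p = 6%, the formula above gives a 5–10% chance of a late death at h = 5–10%, and a fall to zero would mislead little. That stands as a limit on PFS. It is weaker for DOR and duration of CMR, which are confined to responders. The CORAL figures in Protocol 2.1.4 give 77% one-year survival after CR to later salvage, against 2^(−12/6.7) = 29% under the exponential. Neither figure fixes the share progression-free at 2 years, so the plateau remains an assumption. The simulations covered PFS with 36 subjects, not DOR or duration of CMR.

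**The endpoints are descriptive.** PFS and DOR are secondary, and SAP 10.1 also reports the number censored and the pattern of censoring, so a careful reader could detect the artefact. This is correct and limits the importance of the point.

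**Conclusion.** The point holds as a conditional defect of the late curve. SAP 6.2 treats late deaths and late survivors differently, and no rule in the plan corrects this. The effect needs at least one death without recorded progression after the last tumor assessment. Given one, the tail beyond about 26–29 months usually falls to or near zero as an artefact.

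A reader might infer that the tails collapse by construction in every trial. They do not: with no such death the curve is unaffected, and that is the more likely outcome in most of the scenarios examined. The upper quartile is distorted only if the curve is still above 25% at that time, and the median only if it is above 50%.

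The estimates at 12 and 24 months, a median reached earlier, the primary CMR analysis and the sample size are untouched. The frequencies rest on assumed plateaus of 15–40%, assumed late-death rates of 2–10% per year, uniform 12-month enrollment and the follow-up rule in Protocol 7.2.7. If Protocol 3.5.1 governs, the window nearly disappears, although deaths found later in public records could reopen it. The change is inexpensive and should be made before the final curves are seen.

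**What to change.** In SAP 6.2 and 10.5.2, apply one administrative cut-off to PFS, DOR and duration of CMR: 2 years after treatment plus the 14-day visit window, whether or not that visit took place.

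- Count progressions and deaths up to the cut-off as events.
- Censor everyone else at the last evaluable assessment on or before it, including subjects who die later.
- Report no KM estimates beyond it.
- Keep all deaths in OS.

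Duration of CMR has no entry of its own in SAP 6.2 and needs a sentence there. Because Protocol 10.1.1.2 counts death with no time limit, record the change in SAP section 11. The analysis counting all deaths can be kept as a sensitivity analysis. Reconcile Protocol 3.5.1 with 7.2.7 and the Glossary on how long phase 2 subjects are followed.

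The cost is a few sentences and no new data. A few late deaths leave PFS and DOR, and the curves stop at about 2 years after treatment.
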